4.6 Reported toxicity in cervical cancer trials

The standard of care for FIGO stage IB2-IV cervical cancer is concurrent cisplatin and whole-pelvis radiation therapy, followed by brachytherapy [7,16,17,21,25,29]. The addition of chemotherapy improves overall and disease-free survival. With this standard treatment, reported rates of severe (grade 3-4) acute GI toxicity range from 7-25%, GU toxicity from 1-3%, and hematologic toxicity from 5-37% (Table 2). Severe (grade 3-4) late GI toxicity ranges from 3-12% and late GU from 2-17%. The wide range in incidence of toxicity may relate to the use of different grading scales between studies, use of crude toxicity estimates, and variation in quality of patient follow-up. Additionally, treatment varied between trials, with some employing a parametrial radiation boost [17,29] or adjuvant hysterectomy [16], in addition to whole pelvis chemoradiation and brachytherapy.

Depending on the technique, treating the para-aortic nodes and the whole pelvis with concurrent cisplatin, increases rates of acute and late GI toxicity [3,9,32]. In two prospective trials, GOG 125 and RTOG 92-10, patients were treated with concurrent EFRT, 5-FU and cisplatin [9,32]. In both trials, patients received brachytherapy and a parametrial boost to a total dose of 55-65 Gy. In GOG 125, reported grade 3-4 acute (19%) and late GI toxicity rates (14%) were similar to trials treating the whole pelvis with chemoradiation [32] (Table 2). Meanwhile, acute and late GI toxicity rates were much higher in RTOG 92-10 (50% and 34%, respectively), which likely relates to the fact that fractions of radiation were delivered twice daily and para-aortic nodal disease was boosted to total doses of 54 – 58 Gy with 3D conformal technique [9]. At the University of Pittsburg women were treated with concurrent cisplatin and intensity-modulated EFRT, including an IMRT boost to involved lymph nodes to 55-60Gy and a conventional (3D) parametrial boost to 50-60Gy [3]. Two-year toxicity rates were acceptable at 3% and 10% for grade 3-4 acute and late GI toxicity, respectively. Although a follow-up time of two years is short when assessing late toxicity, IMRT holds promise as a technique to deliver EFRT and boost nodal disease with potentially acceptable toxicity.

Table 2- Incidence of Grade 3 or 4 Toxicity with Concurrent Radiation Therapy and Chemotherapy

Study	n	Concurrent chemotherapy	Acute Hemato.	Acute GU	Acute GI	Late GU (year f/u)	Late GI (year f/u)

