8.1.7 Dose Escalation Schema

Dose escalation will operate in the following fashion based on acute DLTs:

1. 3 patients will be accrued to dose level X (starting at level 1)
2. If there are any acute DLTs noted in these initial three participants, and additional three will be accrued (for a total of six).
3. If there is a second acute DLT, accrual will be halted for that cohort, and the dose will be deescalated to level X-1.
4. If 0/3 or 1/6 participants have an acute DLT, after a minimum follow up of 6 weeks, accrual to cohort X+1 may begin.
5. The candidate cohort for MTD will accrue a total of 6 patients. Thus if the dose deescalates, the dose cohort X-1 must have 6 participants before declaration of MTD. Similarly if the protocol proceeds to level 3, then it will accrue 6 participants even if no patient has an acute DLT.

The following schema will be used for late DLTs in conjunction with the above acute rules:

1. Patients will be monitored for late toxicity at every follow-up for 3 years.
2. If a late DLT observed in cohort Y, accrual in that and any higher cohort will be held until there is a minimum of 3 month follow up for all patients.
3. If a second late DLT is observed in cohort Y, then the dose will be de-escalated to Y-1 as per the above schema.
4. If there are no additional late DLTs in cohort Y, then a total of 6 patients must accrue to cohort Y, with a minimum of 3 months follow-up with no further late DLTs before the dose may be escalated to, or for accrual to resume in cohort Y+1.

Of note, acute and late DLTs will be counted separately. Thus if a patient has both an acute DLT and a late DLT, they will be counted as 1 DLT for both schema. If a patient has an acute DLT but not a late DLT, they will only be counted in the acute schema. The only exception will be a patient has an acute

DLT which does not resolve to less than grade 2 by 3 months: these will be counted as both acute and late toxicity for determination of MTD.

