9.0 EVALUATIONS DURING AND AFTER TREATMENT

9.1 Overall Schema

Patients will undergo CT scans prior to treatment as part of the standard staging procedure for gynecologic cancers. Some patients may also undergo PET and/or MRI scans at the discretion of the attending radiation and gynecologic oncologists. Patients will be assessed on a weekly basis, or more frequently as indicated, during the course of therapy by the attending radiation oncologist. During this visit, an interim history and directed physical examination will be performed and treatment-related

toxicity will be prospectively recorded using CTCAE version 4.0. A CBC will be obtained weekly during treatment. Other laboratory work will be obtained as deemed necessary. Cone Beam CT (CBCT) scans will be obtained weekly for the first 2 weeks and then at the discretion of the attending radiation oncologist. Patients will then be evaluated by either gynecologic oncology or radiation oncology every 3 months for follow-up. Assessment for late toxicity at 3-4 months after treatment, and will continue at 6 month interval for 2 years following treatment.

	Pre Treatment	Week 1	Week 2	Week 3	Week 4	Week 5	Follow-up¹
CBC	X	X	X	X	X	X	
Toxicity assessment		X	X	X	X	X	X
CBCT³		X	X	X ²	X ²	X ²	
PET-CT (optional) MRI (optional) for planning	X						

1. Follow-up post radiotherapy for radiation oncology at 4-6 weeks, and every 6 months for 2 years with interval gynecology oncology follow-up (+/- 3 month)
2. Optional
3. Cone beam CT

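### Late toxicity is monitored for 3 years in 8.1.7 but scheduled for 2 in 9.1, and the MTD can be declared with no minimum late follow-up and no stated rule for revising it

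*Combined protocol and SAP*

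**What the plan says.** Section 8.1.7 has two sets of rules, one for acute and one for late DLTs.

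- **Duration.** Late rule 1: "Patients will be monitored for late toxicity at every follow-up for 3 years". Section 9.1, on the same activity: "Assessment for late toxicity at 3-4 months after treatment, and will continue at 6 month interval for 2 years following treatment". Footnote 1 to the 9.1 table: "Follow-up post radiotherapy for radiation oncology at 4-6 weeks, and every 6 months for 2 years". Section 9.1 also provides clinic visits with no stated end: "Patients will then be evaluated by either gynecologic oncology or radiation oncology every 3 months for follow-up".
- **Declaration.** Acute rule 5: "the dose cohort X-1 must have 6 participants before declaration of MTD". It also requires six patients at level 3 if the trial gets that far. It mentions no follow-up time.
- **Late de-escalation.** Late rule 3: "If a second late DLT is observed in cohort Y, then the dose will be de-escalated to Y-1 as per the above schema". It has no time limit and does not mention an MTD already declared.
- **Waiting times.** Acute rule 4 asks for 6 weeks before escalation. Late rule 2 holds accrual after a late DLT until all patients have 3 months of follow-up. Late rule 4, in the same situation, requires six patients "with a minimum of 3 months follow-up with no further late DLTs before the dose may be escalated to" the next level.

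Section 8.1.6, the end of 8.1.7 and Section 11 all make late toxicity an input to the MTD or to de-escalation.

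**The concern.** Two sections give different lengths for the observation period of an endpoint that drives dosing. The rule that fixes the primary result is also a headcount, although half of the toxicity evidence it rests on takes years to appear. The protocol applies a stricter standard to others' data. Of a cited IMRT series it remarks, "Although a follow-up time of two years is short when assessing late toxicity".

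The 3-month waits do not fill the gap. They start only after a late DLT has been seen, and they control accrual and escalation, not declaration. At level 3, the 70 Gy dose in the hypothesis, there is no higher level for late rule 4 to hold back.

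At stake is what a reported MTD means. A reader could not tell whether the dose had survived the late rule or had only been named before that rule could act. Nor could the reader tell whether later events would change it.

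**Working it through.** **Plan's own figure.** Section 11 gives a maximum of 24 patients: 6 × 4 cohorts = 24. It reproduces and is not in dispute.

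**Inputs from the plan.** Accrual is about 4 a year (Section 11), so one entry every 3 months. Two late DLTs in a cohort de-escalate (late rule 3), taken here as two in six. Survival is about 30-40% at 3-4 years (Section 10).

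**Assumptions.** Late exposure starts 6 weeks after treatment ends, as I read 8.1.6. Declaration falls when the sixth patient reaches that point. The plan gives no late-DLT rate, so I use a 3-year risk F of 10%, 20% and 30% without deaths. For orientation only, Table 1 reports late grade 3-4 GI toxicity of 10% to 34%. That is GI alone, whereas a late DLT is GI or GU.

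**Follow-up at declaration, six consecutive patients.** 15, 12, 9, 6, 3 and 0 months: total 45, mean 45/6 = 7.5. None has reached 2 years.

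**Chance that the rule has fired, no deaths.** Constant hazard h = −ln(1 − F)/36 per month, and each patient's risk is 1 − exp(−h·t). Then P0 = exp(−45h), P1 = P0·Σ(exp(h·t) − 1), and P(at least 2) = 1 − P0 − P1.

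- F = 10%: h = 0.00293, P0 = 0.8766, P1 = 0.1173, result 0.6%.
- F = 30%: h = 0.00991, P0 = 0.6403, P1 = 0.3017, result 5.8%.

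With all six followed for 3 years: 1 − 0.9^6 − 6(0.1)(0.9^5) = 11.4%, and 1 − 0.7^6 − 6(0.3)(0.7^5) = 58.0%.

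**With death as a competing event.** Death hazard m = −ln(S)/T, with S = 0.30 or 0.40 and T = 36 or 48 months, independent of late DLT. Each patient's chance of an observed late DLT by t is h/(h + m) × (1 − exp(−(h + m)t)). At 36 months this is 5.9-7.3% for F = 10% and 18.1-22.1% for F = 30%.

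| Six consecutive patients | F = 10% | F = 20% | F = 30% | F = 10%, with deaths | F = 30%, with deaths |
|---|---|---|---|---|---|
| Earliest declaration | 0.6% | 2.5% | 5.8% | 0.4-0.5% | 4.3-4.9% |
| 12 months later | 3.9% | 14.1% | 28.2% | 2.2-2.8% | 17.3-21.2% |
| All followed 2 years | 5.7% | 19.6% | 37.3% | 2.9-3.9% | 21.8-27.5% |
| All followed 3 years | 11.4% | 34.5% | 58.0% | 4.4-6.5% | 29.7-39.7% |

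**Sensitivity, no deaths.**

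- Early onset, with cumulative hazard proportional to the square root of time: 2.2-17.8% at earliest declaration.
- Declaration 6 months later, constant hazard: 2.0-16.3%. The main figures ignore the accrual hold in late rule 2. One hold would add at most about 4 months (5 weeks of treatment plus 3 months), so this range covers it.
- Accrual path: if the lower cohort already held six and six more were then treated above it, the lower cohort has 33, 30, 27, 24, 21 and 18 months (mean 25.5). The chance is then 6.3-39.9%. The same rule therefore carries very different weight depending on the route to declaration.

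**The case against.** **Year 3 is not unobserved.** A reader might infer that late toxicity goes unrecorded in the third year. The text does not support that. The 3-monthly visits have no end date, late rule 1 attaches monitoring to every follow-up, and Section 9.3 calls for toxicity to be documented at each study visit. What stands is that two sections state different durations and no dedicated year-3 assessment is scheduled.

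**Six is necessary, not sufficient.** Rule 5 sets a condition for declaration. It does not order declaration on the day it is met, and the late rules run alongside the acute ones. The end of 8.1.7 also counts an acute DLT not resolved below grade 2 by 3 months as a late one, which implies a 3-month look at those patients. This is fair, and it makes the earliest-declaration figures a lower bound. But no text requires waiting when no late DLT has occurred.

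**Late rule 3 may already continue.** It has no time limit, so it can be read as lowering a declared MTD. That reading is reasonable, but the remedy it names is de-escalation. Once accrual is over there is no one left to de-escalate, and the consequence for the declared dose is unwritten.

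**Complete 3-year follow-up is a generous comparator.** This stands. With Section 10's survival figures, the 3-year chance falls by roughly a third to three fifths, while the chance at declaration barely moves. The gap shrinks but does not close.

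**Conclusion.** The point holds and should be fixed. The duration conflict, the missing minimum late follow-up and the silence on revising a declared MTD are all visible in the text and need no calculation. The duration conflict alone is a small consistency error. The other two matter more, because following the plan as written can fix the primary result before the late rule has had much chance to act.

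The size depends on declaration at the earliest permitted moment, even accrual at 4 a year, a constant hazard and an assumed 10-30% risk. The plan prescribes none of these except the accrual rate.

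Two stronger readings should be resisted. A reader might infer that a low chance of firing means the declared dose is too toxic. The protocol sets no target late-DLT rate, so that does not follow. A reader might also infer that the MTD could fall back to a dose tested in only three patients. Late rule 3 refers back to the acute schema, and rule 5 there requires six before declaration.

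**What to change.** 1. Use one late-toxicity duration in 8.1.7, the 9.1 text and footnote 1. If it is 3 years, add the year-3 toxicity assessments to the schedule.
2. In rule 5 and Section 11, call any dose declared before all six patients have completed that follow-up, died or been lost a provisional MTD.
3. State that late rule 3 continues after declaration, so that a second late DLT in that cohort lowers the MTD to the level below, subject to the six-patient requirement already in rule 5.

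The cost is amendment wording and possibly the year-3 assessments. The provisional MTD comes no later than the MTD would now. The final statement comes up to 2-3 years after the last patient. If the MTD drops to a cohort of three, the top-up that rule 5 already requires takes about 9 months at 4 a year (3 patients × 3 months), plus their own late follow-up. It fits the cap: for example 3 + 3 + 6 = 12 treated through level 3, then 15 after topping up level 2, against 24.

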8.1.8 Treatment Interruptions during RT

The majority of RT-induced side effects requiring treatment breaks will be gastrointestinal in nature and include nausea/vomiting, weight loss, and dehydration. Dietary adjustments, anti-emetic therapy will be pursued. Treatment breaks due to enteritis/proctitis will be given at the discretion of the radiation oncologist. Other reasons for a treatment break will be:

1. Neutropenia with ANC < 500
2. Thrombocytopenia with platelets < 10,000
3. Non-hematologic grade 3-4 toxicity if felt by treating radiation oncologist that a break is necessary (i.e. significant skin reaction).

8.2 Brachytherapy

Brachytherapy is allowed for all patients with an intact uterus. Both LDR and HDR implants are allowed. Both interstitial and intracavitary treatment are also allowed. These will be done as per the standard of care. As a general guideline, the goal of treatment will be to obtain a cumulative dose to the central target, either defined by MR guidance, or by point system (i.e. point A), to 75-95Gy at the equivalent dose at 2 Gy/fraction (EQD2).

Intravaginal boosts will be allowed for patients being treated postoperatively and have evidence of gross or microscopic disease, or for those with cervical involvement from endometrial cancer. The preferred (but not required method) is via HDR, with 3-5 fractions of 4-6Gy per fraction depending on the clinical scenario.

8.3 External Beam Boosting of Primary

In cases where the boosting primary tumor is not achievable with brachytherapy, integrated or sequential IMRT boosting of the disease may be performed to total doses of 55-80Gy depending on the treating physician's discretion, and the standard of care. Irradiation of the primary lesion may be treated at the accelerated dose per fraction of the current dose level, or may be performed at standard dose per fractionation (1.8 – 2.0Gy per fraction). When the total dose of the intended boost exceeds that of the current dose level, the remaining dose must be delivered in a sequential fashion at standard dose per fraction.

8.4 Chemotherapy

Chemotherapy is allowed and preferred on protocol, and is to be administered at the discretion of the treating Gynecologic or Medical Oncologist as per their standard practice.

9.0 EVALUATIONS DURING AND AFTER TREATMENT

9.1 Overall Schema

Patients will undergo CT scans prior to treatment as part of the standard staging procedure for gynecologic cancers. Some patients may also undergo PET and/or MRI scans at the discretion of the attending radiation and gynecologic oncologists. Patients will be assessed on a weekly basis, or more frequently as indicated, during the course of therapy by the attending radiation oncologist. During this visit, an interim history and directed physical examination will be performed and treatment-related

toxicity will be prospectively recorded using CTCAE version 4.0. A CBC will be obtained weekly during treatment. Other laboratory work will be obtained as deemed necessary. Cone Beam CT (CBCT) scans will be obtained weekly for the first 2 weeks and then at the discretion of the attending radiation oncologist. Patients will then be evaluated by either gynecologic oncology or radiation oncology every 3 months for follow-up. Assessment for late toxicity at 3-4 months after treatment, and will continue at 6 month interval for 2 years following treatment.

	Pre Treatment	Week 1	Week 2	Week 3	Week 4	Week 5	Follow-up¹
CBC	X	X	X	X	X	X	
Toxicity assessment		X	X	X	X	X	X
CBCT³		X	X	X ²	X ²	X ²	
PET-CT (optional) MRI (optional) for planning	X						

1. Follow-up post radiotherapy for radiation oncology at 4-6 weeks, and every 6 months for 2 years with interval gynecology oncology follow-up (+/- 3 month)
2. Optional
3. Cone beam CT

9.2 Criteria for Going Off Protocol

- 9.2.1. Development of local, regional, or distant progression during treatment.
- 9.2.2. Intolerable side effects from therapy despite in spite of measures to ameliorate them.
- 9.2.3. Noncompliance with protocol requirements.
- 9.2.4. Patient refusal or withdrawal of consent.
- 9.2.5. Discretion of PI or treating physician.

9.3 Reporting Adverse Events

For all possible treatment related adverse events/toxicities reported or observed, the information should be recorded in the patient's medical record and on the study's Toxicity Evaluation Form or in the study's toxicity database. This should include a description of the event, its severity grade, the relationship to the study treatment and the onset date.

CRITERIA FOR REPORTING REQUIREMENTS FOR SERIOUS ADVERSE EVENTS THAT OCCUR WITHIN 30 DAYS OF THE DATE OF THE LAST PROTOCOL TREATMENT

	Grade 3 or 4	Grade 4	Grade 4 & 5 Unexpected
	With Hospitalization	Without Hospitalization Expected	

Unrelated, Unlikely	Not required	Not required	10 Calendar Days
Possible, Probable or Definite	Unexpected 10 Calendar Days	Not required	5 Calendar Days

Any late death (> 30 days after end of radiation) attributed to the protocol treatment should be reported within 5 calendar days of discovery

Treatment-related toxicity and adverse events should be documented in a routine manner at each study visit. Timely reporting of serious adverse events should be followed per DUHS IRB requirements. Because of the medical importance of serious and/or unexpected adverse events, the PI and study staff should review any expedited report prior to submission to the DUHS IRB.

Definitions for Adverse Event Reporting

Study therapy - Study therapy is the required treatment or procedure as defined by the protocol.

Expected events - Expected events are those that have been previously identified as resulting from treatment of gynecologic cancer with radiation therapy and chemotherapy. For purposes of this study, an adverse event is considered unexpected when either the type of event or the severity of the event is not listed in the protocol informed consent.

For purposes of this study, reporting requirements are determined by the assessment of the following adverse event characteristics: the type or nature of the event; the severity (grade); the relationship to the study therapy and whether the event is expected or unexpected.

For purposes of this study, grade 1 lab abnormalities will not be considered significant and thus, will not be captured as AEs. Only lab abnormalities greater than grade 1 and related to the treatment under study will be captured.

The recommended assessment steps include:

- Weekly appraisal of the patient during treatment.
- Identification of adverse events using the NCI CTCAE Version 4.0 terminology. A copy of the CTCAE can be downloaded from the CTEP home page (<http://ctep.cancer.gov>).
- Grading the severity of the adverse event using the NCI CTCAE Version 4.0.
- Determination as to whether the adverse event is related to the study therapy using the following categories: Unrelated, Possible, Probable, and Definite.
- Determine whether the adverse event is expected or unexpected.

10.0 RISKS/BENEFIT ASSESSMENT

Patients with locally-advanced gynecologic cancers are at high risk of relapse and death. Long-term (3-4 years) survival is ~30-40% in patients with good performance status. Local failure after concurrent chemotherapy and radiation therapy occurs in ~40-50% of patients. Thus, increasing the intensity of RT is rational and may improve clinical outcomes for these patients.

The expected acute side effects of RT to the pelvis include fatigue, skin erythema, enteritis, proctitis, and cystitis. The incidence of acute grade 3-4 enteritis / proctitis with conventional therapy is 20-35% of

patients, while that of hematologic toxicity is 20-40% and cystitis is 5%. It is possible that the risk of severe enteritis / proctitis (requiring treatment breaks, intravenous fluids, hospitalization, etc.) will be greater with increased radiation boost dose. We will attempt to avoid this by utilizing IMRT, which can better spare normal tissues from the high dose component of treatment. In addition, it is possible that the use of IMRT (which can potentially increase the volume of normal tissues getting a low dose of RT) will increase the risk of acute side effects. The patients will be monitored weekly during RT and regularly after treatment to evaluate these toxicities and determine the maximum tolerated dose.

11.0 STATISTICAL CONSIDERATIONS

The maximum sample size of this study is 24 (6 patients at each of the 4 dose cohorts). The accrual rate is estimated to be about 4 patients per year. The dose-limiting toxicities are defined in Section 9.1.6 The dose cohorts and the dose escalation rules are defined in Section 9.1.5 and 9.1.7 respectively. These sections show that there are separate and independent dose escalation rules for early DLT's (toxicities that occur in the first 4 weeks of treatment) and late DLT's (toxicities that occur after 4 weeks). Likewise, there are separate definitions of dose-limiting toxicity for early and late toxicities. Thus, the trial could de-escalate due to either early or late toxicities. Because of the independence of the two sets of rules, a dose cohort of 6 patients in which one patient has an early DLT and one patient has a late DLT would not result in de-escalation of the dose. If a patient has both an early and a late DLT, the dose escalation rules would treat these DLT's as if they happened to two different patients.

Toxicities will be tabulated within each dose cohort by type, grade, and whether they were early or late. All toxicities will also be evaluated for their relationship to treatment and whether they were expected or unexpected. Time to local-regional recurrence (TTLR), time to distant recurrence (TTDR), disease-free survival (DFS), and overall survival (OS) will be estimate in all patients using the Kaplan-Meier method. TTLR will be defined as the time from first radiation treatment to local or regional (nodes) recurrence, whichever comes first, ignoring distant failures and censoring deaths. TTDR will be defined as the time from first radiation treatment to distant recurrence, ignoring local and regional failures and censoring deaths. DFS will be defined as the time from first radiation treatment to any recurrence (local, regional, or distant) or death, whichever comes first. OS will be defined as the time from first radiation treatment to death due to any cause.

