8.1.6 Dose Limiting Toxicities (DLTs)

The National Cancer Institute’s Common Terminology Criteria for Adverse Events (CTCAE), version 4.0 will be used to score and grade treatment-related toxicity.

Two distinct toxicities are to be considered in this protocol: acute and late. These types of toxicity are distinct in terms of time of onset, character, management, and expected course, thus they will be considered separately for the purposes of determining the MTD.

Since integrated radiation dose escalation is unlikely to substantially affect the hematopoietic system, only non-hematologic, grade 3-4, acute toxicity will be considered the primary dose-limiting toxicity (acute DLT).

Acute DLT will be defined based on the side effects inherent from radiation therapy for gynecologic cancers, including effects on bowel, bladder, and skin. Dose limiting toxicity will include any of the following during treatment or within 6 weeks of completion:

1. Acute Grade 3-4 enteritis or proctitis requiring:
 - a. Tube feedings
 - b. Total parenteral nutrition
 - c. Hospitalization secondary to inadequate oral caloric or fluid intake
 - d. Prolonged treatment breaks secondary to enteritis (> 1 week)

e. Life-threatening consequences such as bowel perforation, obstruction, or bleeding requiring transfusion.

2. Acute Grade 3-4 bladder toxicity
 - a. Bladder ulceration or necrosis
 - b. Grade 3-4 cystitis including hematuria requiring transfusion
 - c. Urinary obstruction not due to clot passage
3. Grade 4 dermatologic toxicity (skin necrosis or ulceration of full thickness of dermis)

Late DLTs will be defined at grade 3-4 GI or GU toxicity with onset after 6 weeks of treatment. The CTCAE v 4.0 will be used for determination of late toxicity grade, with one exception: the use of plasma coagulation or similar procedure for rectal bleeding will not be considered a late DLT, even though it is considered a grade 4 toxicity by the CTCAE. If however, there are other consequences of radiation proctitis which meeting grade 3-5 criteria, this will be considered a late DLT.

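### Section 11 misstates the acute/late DLT boundary of 8.1.6 (4 weeks of treatment instead of 6 weeks after completion), and for some pairs of DLTs this reverses the dose decision

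*Combined protocol and SAP*

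**What the plan says.** Section 11 (Statistical Considerations) defers to other sections: "The dose-limiting toxicities are defined in Section 9.1.6", with the cohorts and escalation rules placed in 9.1.5 and 9.1.7. It continues: "These sections show that there are separate and independent dose escalation rules for early DLT's", glossing early as "toxicities that occur in the first 4 weeks of treatment" and late as "toxicities that occur after 4 weeks". It adds that a six-patient cohort in which "one patient has an early DLT and one patient has a late DLT would not result in de-escalation of the dose".

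Section 9.1 has no numbered subsections. The dose levels, DLT definitions and escalation rules are in 8.1.5, 8.1.6 and 8.1.7. For acute events 8.1.6 says: "Dose limiting toxicity will include any of the following during treatment or within 6 weeks of completion". For late events it says: "Late DLTs will be defined at grade 3-4 GI or GU toxicity with onset after 6 weeks of treatment".

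Under 8.1.7 the two types are counted separately, and a second DLT of the same type in a cohort triggers de-escalation. An acute DLT that has not fallen below grade 2 by 3 months counts in both tallies.

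**The concern.** The two boundaries are about seven weeks apart. A DLT in week 5, with the patient still on radiotherapy, is acute under 8.1.6 and late under Section 11. The maximum tolerated dose is the primary objective. Because the tallies are not pooled, moving one event from one tally to the other can create or remove the second DLT that forces de-escalation. Section 11 also tabulates toxicities as early or late, so reporting is affected. No statement says which section governs if they differ, and the cross-reference that would settle it points to sections that are not there.

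The late definition in 8.1.6 is loose as well. Its 6 weeks can be read from the start or from the completion of radiotherapy. Read from the start, GI or GU events between week 6 and about week 11 are both acute and late. Neither reading gives a 4-week boundary.

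**Working it through.** **Plan's own figure.** Maximum sample size: 6 patients × 4 cohorts = 24, as Section 11 states.

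**Windows.** 8.1.5 gives 25 fractions at 5 per week, so 25/5 = 5 weeks. Adding 6 weeks puts the end of the acute window at about week 11 from the start, if completion means the last of these fractions. The disputed span is 11 − 4 = 7 weeks.

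**Pairs of DLTs.** Take two DLTs in different patients of one cohort, both GI/GU and both resolving in time, with the late window of 8.1.6 starting 6 weeks after completion.

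| Onset of the two DLTs | 8.1.6 | Section 11 | Same decision? |
|---|---|---|---|
| weeks 1-4, weeks 1-4 | 2 acute: de-escalate | 2 early: de-escalate | yes |
| weeks 1-4, weeks 5-11 | 2 acute: de-escalate | 1 early + 1 late: no | **no** |
| weeks 1-4, after week 11 | 1 acute + 1 late: no | 1 early + 1 late: no | yes |
| weeks 5-11, weeks 5-11 | 2 acute: de-escalate | 2 late: de-escalate | yes |
| weeks 5-11, after week 11 | 1 acute + 1 late: no | 2 late: de-escalate | **no** |
| after week 11, after week 11 | 2 late: de-escalate | 2 late: de-escalate | yes |

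- Weeks 3 and 8 illustrate row 2. The difference disappears if the week-3 event is unresolved at 3 months, because it then counts as late too.
- Weeks 5 and 26 illustrate row 5. The week-5 event must be GI/GU and must fall below grade 2 by 3 months. This example holds whether the 6 weeks in the late definition run from the start or from completion. With week 8 in place of week 5, it holds only if they run from completion.

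**Illustrative frequency in a full cohort of six.** Inputs:

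- p, acute-window DLT rate: 3% (IMRT nodal-boost series, 1 of 36, Sections 4.6 and 4.8) up to 20-35% (conventional therapy, Section 10), with 10% between. These are grade 3-4 GI rates standing in for DLTs.
- q, share of acute-window DLTs that start in weeks 1-4: 20-50%. This is an assumption; the documents give no figure.
- r, DLT rate after week 11, independent of the acute event: 0-14% (Section 4.6 reports late GI rates of 10% and 14%).

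The two rules disagree in two ways:

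- Only 8.1.6 de-escalates: 30 p² q(1−q)(1−p)⁴(1−r)⁵
- Only Section 11 de-escalates: 30 p(1−q)(1−p)⁵ r(1−r)⁵

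The factor 30 = 6 × 5 is the number of ordered pairs of patients. The lowest and highest sums over the grid are:

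- p = 3%. Low (q = 0.2, r = 0): 30 × 0.0009 × 0.16 × 0.97⁴ = 0.0038. High (q = 0.2, r = 0.14): 0.0018 + 0.0407 = 0.0425.
- p = 10%. Low (q = 0.2, r = 0): 30 × 0.01 × 0.16 × 0.9⁴ = 0.0315. High (q = 0.2, r = 0.14): 0.0148 + 0.0933 = 0.1081.
- p = 20-35%. Low (p = 0.20, q = 0.2, r = 0): 30 × 0.04 × 0.16 × 0.8⁴ = 0.0786. High (p = 0.35, q = 0.5, r = 0): 30 × 0.1225 × 0.25 × 0.65⁴ = 0.1640.

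An exact enumeration over the grid gives the same ranges. If a quarter of acute DLTs are unresolved at 3 months, each figure falls by a quarter; the last range becomes 0.059-0.123.

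**The case against.** The strongest reply is that Section 11 sets no rule of its own. It points elsewhere for the definitions and only paraphrases them; 8.1.6 is itemised and operative. The visits at 4-6 weeks and 3-4 months after treatment in Section 9.1 also fit 8.1.6. This stands: a team that follows 8.1.6 makes no wrong decision. A reader might take 8-16% as the chance of a wrong dose decision in this trial. The documents do not support that, because the figure applies only if Section 11 is followed instead, and nothing says how likely that is.

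The inputs are soft, which also stands. The timing split has no source. The acute GI DLT list in 8.1.6 is narrower than grade 3-4 enteritis or proctitis, and for the closest technique the range is only 0.4-4%. The late rates come from follow-up of 1.5 to 4 years, so they overstate what would be seen by the time of escalation.

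Two further inferences are tempting:

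- That a single GI/GU DLT in weeks 5-11 always changes the accrual hold and the follow-up needed before escalation. If the late window of 8.1.6 runs from the start of radiotherapy, such an event in weeks 7-11 is already late under 8.1.6, and the 3-month requirements apply under both sections.
- That a grade 4 skin DLT in weeks 5-11 is lost from both tallies. This follows only if Section 11's timing is combined with the GI/GU-only late definition of 8.1.6; under 8.1.6 alone it is an acute DLT.

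Finally, week 11 is not general. Sections 8.1.3, 8.1.5, 8.2 and 8.3 allow brachytherapy or a sequential boost after the 25 fractions. If completion includes these, the acute window ends later.

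**Conclusion.** The inconsistency is real and should be fixed. Section 11 gives a wrong boundary for a rule that sets the primary output, and its cross-references lead nowhere. Two of six timing patterns give opposite decisions, one in each direction. In the first, Section 11 would keep a dose that 8.1.6 rejects.

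The finding rests on the text alone. The size is an illustration: about 0.4-4% of full six-patient cohorts at an acute DLT rate of 3%, 3-11% at 10%, and 8-16% at 20-35%. It is conditional on Section 11 being applied, on the assumed timing split, on all DLTs being GI/GU and resolving in time, and on a late window starting 6 weeks after completion. No range is given for a late window read from the start of radiotherapy, because it would depend on how events in weeks 5-11 divide around week 6, which the documents do not say.

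The case for acting although the intent can be inferred is practical. With at most six patients per cohort and about four accrued per year, the tally to which one DLT is assigned can determine the declared dose.

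**What to change.** - Section 11: replace both 4-week glosses with the 8.1.6 windows, and correct the references to 8.1.5, 8.1.6 and 8.1.7. Correct the reference to 9.1.7 in 8.1.5 as well.
- 8.1.6: define a late DLT as grade 3-4 GI or GU toxicity with onset more than 6 weeks after completion, so that each new GI/GU event enters one tally. Keep the existing exception for coagulation of rectal bleeding, and the 8.1.7 rule that an unresolved acute DLT counts in both.
- 8.1.7: run the 6-week minimum follow-up before escalation from the same point.
- State once whether completion means the last of the 25 IMRT fractions or the last brachytherapy or sequential boost, and use that anchor throughout.

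This is a wording amendment only. The maximum sample size stays 24.
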